Study Protocol

“Does Antrum Size Matter in Sleeve Gastrectomy?”

Study Protocol

“Does Antrum Size Matter in Sleeve Gastrectomy? ”

BACKGROUND

Laparoscopic sleeve gastrectomy (LSG) is currently the most frequent primary bariatric procedure performed worldwide. LSG is safe and effective in terms of excess weight loss. It is a powerful metabolic operation that activates significant hormonal pathways that lead to changes in eating behavior, glycemic control and intestinal functions. LSG can be a faster procedure for its technical aspects (any need for intestinal anastomosis, being limited to the stomach transection). The most frequent and sometimes dangerous complications are leaking, hemorrhage, splenic injury, stenosis and Gastroesophageal Reflux Disease (GERD)(1). Despite its established efficacy and safety, dispute still exists on optimal operative technique for LSG: bougie size, distance of resection margin from the pylorus, the shape of section at the gastroesophageal junction, staple line reinforcement and intraoperative leak testing are among the most controversial issues (2). Indeed, different Authors have adopted a resection distance from the pylorus between 2 and 6–7 cm with various reasons (3). In favor of resections more distant to the pylorus, Authors argue that it seems to improve gastric emptying, prevent distal stenosis and reduce intraluminal pressure, potentially leading to a lower incidence of fistula and/or reflux. On the other hand, resections close to the pylorus seems to reduce more the gastric distensibility and increase intragastric pressure, potentially leading to a better satiation with less oral intake (4, 5). However, only few studies have investigated the differences between these two approaches (3). Thus, the primary aim of this randomized monocentric study is to evaluate variations in percentage of excess weight loss (%EWL) at 1 and 2 years follow-up after LSG in subject with a gastric resection starting from 2 cm from the pylorus (wide antrectomy) compared to those with a gastric resection starting from 6 cm from the pylorus (small antrectomy). Secondary aim-points are represented by evaluation of differences in morbidity, mortality, tolerance to food, incidence of reflux symptoms and GERD Health-Related Quality-of-Life (GERD-HRQL) score between the two groups.

Material and Methods

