2.2 Study Design

The study is designed as a randomized controlled trial. Primary outcome was the evaluation of %EWL between 2 groups. Secondary outcomes were evaluation of morbidity, mortality, incidence of reflux symptoms and Quality of Life score between the Groups.From January 2015 to November 2017, a series of 218 consecutive patients suffering from morbid obesity and scheduled for LSG were included; informed consent was obtained from each participant before surgery.

Inclusion criteria were morbid obesity defined as BMI 40 kg/m² and age between 25–50 years old. Obesity-related comorbidities included Type 2 Mellitus Diabetes (T2MD), hypertension, hyperlipidemia, bronchial asthma, osteoarthritis and degenerative joint disease.

Exclusion criteria

Patients with previous bariatric surgical procedures, endocrine disorders causing obesity (as hypothyroidism and Cushing disease), pregnancy or lactation, psychiatric illness, or recent diagnosis of malignancy, inflammatory bowel disease, Barrett's esophagus, and GERD with esophagitis scored as or greater than grade B, a large hiatal hernia (>3 cm) were excluded from the study. In case of absence or grade A esophagitis, GERD was also considered as severe with GERD-HRQL > 30 and when interfering with daily activities or inducing dietary restriction despite, also these were excluded.

One hundred-fifty patients were considered eligible and randomized in two Group (Group A n = 75, Group B n=75). All patients underwent elective laparoscopic LSG. In the case of conversion to open surgery, patients were excluded. Details of enrollment procedure are shown in Fig. 1.

Randomization

Participants were randomly assigned to one of the two groups using computer-generated permuted blocks (www.randomization.com). Outpatient clinic controls were done by surgeons/surgical residents/GP blinded for the groups. Patients were randomized into 2 groups based on the distance to pylorus of resection: Group A (n=75) at 2 cm, Group B(n=75) at 6 cm. Results were obtained at 1 and 2 years follow-up. The randomization scheme was generated using the web site Randomization.com (<http://www.randomization.com>).

Blinding Process

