2.5 Post-operative evaluation

All patients were actively clinical followed up regularly at 3, 6, 12 and 24, included GERD-HRQL. UE was performed in all patients at 12 or 24 months. Significant vomiting and food intolerance were evaluated at 6, 12 and 24 months follow-up. Vomiting was considered significant when occurring at least three times a week and food intolerance was defined as vomiting occurring almost each day. Esophageal biopsies were performed only in case of esophagitis \geq B (9).

Weight loss parameters were recorded at 3, 6, 12 and 24 months after the LSG : BMI (in kg/m²), %EWL and percentage total weight loss %TWL from baseline. The secondary endpoints were GERD and esophagitis studied with Upper endoscopy and GERD score

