2.6 Statistical Analysis

Statistical analysis was performed using Graphpad Quick Calcs (GraphPad version 6.04 for Windows, GraphPad Software, La Jolla California USA). Baseline comparisons were performed using chi-square tests and T-tests. Continuous variables are expressed as mean \pm standard deviation (SD). Differences between preoperative and postoperative parameters were compared by Wilcoxon paired rank test. For all tests, a two-sided $p < 0.05$ was considered statistically significant.

Sample size

THIS IS A CONTROLLED RANDOMIZED STUDY OF BINARY NON-INFERIORITY OUTCOME IN PARALLEL GROUPS. IF THERE IS TRULY NO DIFFERENCE BETWEEN THE STANDARD AND EXPERIMENTAL TREATMENT, THEN 138 PATIENTS ARE REQUIRED TO BE 90% SURE THAT THE LOWER LIMIT OF A ONE-SIDED 95% CONFIDENCE INTERVAL (OR EQUIVALENTLY A 90% TWO-SIDED CONFIDENCE INTERVAL) WILL BE ABOVE THE NON-INFERIORITY LIMIT OF -10. SAMPLE SIZE WAS CALCULATED WITH SEALED ENVELOPE LTD. 2012.

Appendix 2

Chief Investigator: [name], PhD – UOC Chirurgia Generale – Ospedale A. Rizzoli –

Lacco ameno napoli. [contact]; cellulare: [name].

Results summarized in the table:

Table 1 :Preoperative demographics data

Table 2: Weight, Body mass index, and the percentage of excess body weight loss and the Percentage Total Weight loss of the two groups at follow-up 3-6-12-24-months

Table 3: GERD Health-Related Quality-of-Life (GERD-HRQL) Score preoperative and postoperative scores follow-up 3-6-12-24 months

Table 4: Endoscopy Preoperative and at 1 and 2 years follow-up into two Groups

Table 1 Preoperative demographics data

Patients	Total	Group A (n=75)	Group B(n=75)
Age	33.6 ± 14	32.2 ± 8	34.2 ± 9
Male	39%	35%	38%
Female	61%	63%	62%
Height	151.2 ± 22	150.1 ± 23	152.8 ± 33
Weight kg	121.9 ± 21.7	124.5 ± 26.7	125.3 ± 23.5
BMI	44.23 ± 6.32	43 ± 8 (40–57)	44 ± 4(40–55)
ASA(I-II)(%)	65%	64%	66%
ASA(III-IV)(%)	35%	36%	34%
T2MD(%)	12(8.%)	7(9.3%)	5(6.6%)
Chronic obstructive pulmonary disease(%)	7(4.6%)	2(2.6%)	3(4%)
Heart Ischemia	1	0	0
Hypertension(%)	95(63%)	55(73.3%)	40(53.4%)

BMI body mass index, %EWL percentage excess weight loss, %TWL percentage total weight loss, Type 2 Mellitus Diabetes (T2MD)

Table 2: Weight, Body mass index, and the percentage of excess body weight loss and the Percentage Total Weight loss of the two groups at follow-up

Patients	3 months follow-up		p	6 months follow-up		p	12 months follow-up		p	24 months follow-up		p
	145/150			141/150			136/150			131/150		

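### Secondary outcomes are judged by an unadjusted two-sided 0.05 rule: Table 3 gives 20 verdicts, with one reflux score tested as three dependent bands, and the counts support far fewer claims than are printed

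*Combined protocol and SAP*

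**What the plan says.** Section 2.6 has a single decision rule: "For all tests, a two-sided $p < 0.05$ was considered statistically significant". The only tests it names are for other purposes. For baseline it says "Baseline comparisons were performed using chi-square tests and T-tests", and a Wilcoxon paired test is named for change from before to after surgery. No between-group test is named for postoperative outcomes.

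The secondary outcomes are listed in three places, and the lists differ:
- Background: "Secondary aim-points are represented by evaluation of differences in morbidity, mortality, tolerance to food, incidence of reflux symptoms and GERD Health-Related Quality-of-Life (GERD-HRQL) score".
- Section 2.2: "Secondary outcomes were evaluation of morbidity, mortality, incidence of reflux symptoms and Quality of Life score between the Groups".
- Section 2.5: "The secondary endpoints were GERD and esophagitis studied with Upper endoscopy and GERD score".

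None of these ranks the outcomes, names a deciding visit for them, or marks any as exploratory. On timing, section 2.5 says "All patients were actively clinical followed up regularly at 3, 6, 12 and 24, included GERD-HRQL" and, separately, "Significant vomiting and food intolerance were evaluated at 6, 12 and 24 months follow-up". Table 3 nevertheless reports vomiting and food intolerance at 3 months as well. Its five rows are GERD-HRQL <15, >16<30 and >31, significant vomiting, and intolerance to food. Each row carries a p label at 3, 6, 12 and 24 months.

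**The concern.** Reflux and food tolerance are what the Background weighs against weight loss, so the secondary claims matter to how the trial is read. Under the rule in 2.6, any one of 20 cells falling below 0.05 is enough for a claim that one resection distance is worse. Cutting one 0-50 score into three bands makes this worse, because a single shift in the score can be counted up to three times at a visit. Esophagitis (Table 4), morbidity and mortality enlarge the family further. At stake is which secondary statements can be made, and at which visits. The primary outcome, %EWL, is not touched.

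**Working it through.** **1. Number of tests.** Table 3: 5 rows × 4 visits = 20 labelled cells. On the section 2.5 schedule the count is 3 bands × 4 visits + 2 outcomes × 3 visits = 18. Food intolerance at 12 and 24 months is 0 vs 0, so those two cells cannot be tested. The three bands sum exactly to n at 3, 6 and 12 months, so they are dependent. At 24 months they sum to 64 and 65 against n of 65 and 66.

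**2. Family-wise error with no true difference.** The documents state no such figure, so there is none to reproduce.
- Independent tests: 1 − 0.95^20 = 0.64; for 18 tests, 1 − 0.95^18 = 0.60.
- Equicorrelated normal statistics, share of draws with max|z| > 1.96, 20 tests: 0.54, 0.42, 0.29 and 0.16 at assumed correlations of 0.3, 0.5, 0.7 and 0.9. For 18 tests at 0.5: 0.40.
- Null simulation of the Table 3 cells (pooled printed rates, about 70 per group, assumed correlation between visits from 0 to 0.9): 0.36-0.47 with uncorrected chi-square. With Fisher it is roughly 0.2-0.3, the value depending on whether the food-intolerance row is included and on the correlations assumed.

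**3. What the printed counts support.** Fisher p from the Table 3 counts, with denominators 72/73, 70/71, 67/69 and 65/66. An asterisk marks a cell labelled P<0.05 in the table.

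| Row | 3 mo | 6 mo | 12 mo | 24 mo |
|---|---|---|---|---|
| Score <15 | 0.0016* | 0.0008* | 0.24* | 0.29* |
| Score >16<30 | 0.012* | 0.0037* | 0.53 | 0.37 |
| Score >31 | 0.12* | 0.21* | 0.20* | 0.50* |
| Vomiting | 0.026* | 0.17* | 0.16* | 0.62* |
| Food intolerance | 0.24* | 0.50 | 0 vs 0 | 0 vs 0 |

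Fifteen cells are labelled P<0.05 (5, 4, 3 and 3 by visit). Five are below 0.05 on the counts, by Fisher or uncorrected chi-square. The other ten have Fisher p from 0.12 to 0.62.

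**4. Holm over the 20 cells.** Multiply the ordered p-values by 20, 19, 18 and so on:
- score <15 at 6 months: 0.00076 × 20 = 0.015
- score <15 at 3 months: 0.00165 × 19 = 0.031
- score >16<30 at 6 months: 0.00365 × 18 = 0.066
- score >16<30 at 3 months: 0.0117 × 17 = 0.20
- vomiting at 3 months: 0.0264 × 16 = 0.42

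Two cells remain. Uncorrected chi-square keeps the same two (0.012 and 0.026).

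**5. One test of the score per visit.** A rank test on the three printed bands gives p = 0.001, 0.0006, 0.17 and 0.24 at 3, 6, 12 and 24 months (the last on the 64 and 65 patients in a printed band). Holm over four visits: 0.003, 0.002, 0.34 and 0.34.

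**6. Esophagitis, from Table 4.** Grade B or worse at 1 year: (11+2)/53 = 13/53 vs 5/55, Fisher p = 0.040. At 2 years: (9+1)/52 = 10/52 vs 3/53, p = 0.042. In a Holm family of six (four score tests, two esophagitis tests), the score at 6 and 3 months gives 0.003 and 0.005. The smaller esophagitis p becomes 0.040 × 4 = 0.16, and the other takes the same value.

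**The case against.** Four objections have weight.

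**The error rate has no single value.** A reader might infer a flat 40%. That needs an assumed correlation near 0.5, or uncorrected chi-square on sparse cells. Fisher tests give about half to two-thirds of it, and the equicorrelated model suits mutually exclusive bands poorly. This stands, so only a range should be quoted. The lowest figure, 0.16, is still about three times 0.05.

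**Most unsupported claims are not a multiplicity problem.** A reader might infer that the missing adjustment produced a few isolated early differences. Table 3 does not show that: 15 of 20 cells are labelled P<0.05, six of them at 12 or 24 months. Re-testing at plain 0.05 removes ten labels; Holm removes three more. This stands, and the label error has to be corrected in its own right. Correcting it would still leave five nominal claims, three of which fail Holm over 20.

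**The early reflux signal survives.** A reader might infer that it is a chance finding. The counts say otherwise, both in the 20-cell Holm and in the one-test-per-visit analysis.

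**Any family chosen now is chosen after seeing the data.** Also true. Making GERD-HRQL the only family would leave out esophagitis, which section 2.5 names as a secondary endpoint. The documents also contain no concluding text, so it cannot be said that the sponsor has presented these differences as established.

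**Conclusion.** The point holds within limits. The plan has no control, order or exploratory label for its secondary tests, and it tests one score three times per visit. The false-claim probability for Table 3 is about 0.16 to 0.64, depending on the correlation and the test, neither of which the documents supply.

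On the printed counts:
- An early GERD-HRQL difference, at 3 and 6 months, is supported after adjustment.
- No GERD-HRQL difference is demonstrated at 1 or 2 years.
- The esophagitis difference at 1 and 2 years is exploratory (unadjusted p about 0.04 each) and would not survive the six-test Holm family.
- The 3-month vomiting difference is nominal only.

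The p-values rest on the table's counts being correct. The set that survives depends slightly on the family: uncorrected chi-square with Holm over 18 also admits the middle band at 6 months (0.00303 × 16 = 0.048). That is the same score at the same visit, so the conclusion does not change.

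**What to change.** In section 2.6:
1. Limit the confirmatory 0.05 rule to the primary outcome.
2. Name the between-group test for postoperative outcomes. Compare GERD-HRQL once per visit, as the score itself or as one ordinal variable, instead of band by band.
3. Report vomiting, food intolerance, esophagitis, morbidity, mortality and any other secondary as group differences with 95% confidence intervals, labelled exploratory and without significance verdicts.
4. If a formal secondary claim is wanted, define one Holm family that includes the esophagitis endpoint named in section 2.5.
5. State that the rule was added after the data were seen.

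Separately, recompute and correct the p labels in Table 3, and reconcile the 3-month vomiting and intolerance cells with the schedule in section 2.5.

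The cost is a few lines of text and a re-run on existing data, with no new patients or visits. The downside is that some nominally significant differences, such as 3-month vomiting, become descriptive.

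### The 138 patients and 90% power are stated for a binary non-inferiority outcome, but the primary outcome is continuous %EWL with no stated primary hypothesis, so the power cannot be verified

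*Combined protocol and SAP*

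**What the plan says.** The sample-size paragraph of section 2.6 contains four elements:

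- Design and outcome type: "THIS IS A CONTROLLED RANDOMIZED STUDY OF BINARY NON-INFERIORITY OUTCOME IN PARALLEL GROUPS".
- Assumed effect: "IF THERE IS TRULY NO DIFFERENCE BETWEEN THE STANDARD AND EXPERIMENTAL TREATMENT".
- Size, power and confidence level: "THEN 138 PATIENTS ARE REQUIRED TO BE 90% SURE THAT THE LOWER LIMIT OF A ONE-SIDED 95% CONFIDENCE INTERVAL", which the paragraph equates with a 90% two-sided interval.
- Margin: "WILL BE ABOVE THE NON-INFERIORITY LIMIT OF -10", with no unit.

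The calculator's supplier is named, but none of the values entered into it are given.

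Elsewhere the outcome is different. The Background says that the primary aim is to "evaluate variations in percentage of excess weight loss (%EWL) at 1 and 2 years follow-up after LSG". Section 2.2 says: "Primary outcome was the evaluation of %EWL between 2 groups".

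The analysis paragraph of section 2.6 names two uses of tests: "Baseline comparisons were performed using chi-square tests and T-tests" and "Differences between preoperative and postoperative parameters were compared by Wilcoxon paired rank test". It applies a two-sided 5% level to every test. Table 2 gives excess weight loss (labelled EBWL%, read here as %EWL) as mean ± SD by group, with p printed only as below or above 0.05.

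**The concern.** A power statement means something only for a given outcome, hypothesis and decision rule. Here the sizing paragraph describes a binary outcome and a non-inferiority question. The rest of the document describes a continuous outcome and does not say whether the trial succeeds by showing a difference or by excluding a deficit of a given size.

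The missing inputs make this worse. Without a rate or SD, 138 cannot be recomputed. Without a unit, -10 could be percentage points of a responder rate or points of %EWL. Without knowing whether the 2 cm or the 6 cm group is experimental, the direction of the margin is undefined. With two primary time points and no rule for them, it is unclear which result decides.

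At stake is what the trial can conclude. The 24-month %EWL result is printed only as p>0.05. A non-significant difference test does not by itself establish non-inferiority, which is the question the trial was sized for. The interval that would answer that question is not reported.

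**Working it through.** **Inputs.** From section 2.6: 138 patients in total, 90% power, one-sided 5%, margin 10, true difference 0. From section 2.2: equal groups, so 69 per arm. Not given: event rate, SD, unit of the margin. The plan's figure therefore cannot be reproduced forwards, only solved backwards. The formulas below are the usual normal approximations, rounded up per arm. The calculator's own method is not in the documents.

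f = (1.645 + 1.282)² = 8.564.

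**Binary reading, margin 0.10.** n per arm = 2 × f × p(1 − p) / 0.10².

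| Assumed rate p | n per arm | Total |
|---|---|---|
| 0.80 | 275 | 550 |
| 0.90 | 155 | 310 |
| 0.95 | 82 | 164 |
| 0.958 | 69 | 138 |

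The formula is symmetric in p and 1 − p, so 138 needs a rate of about 96% or about 4%. With 69 per arm, power would be 43% at a rate of 0.80, 62% at 0.90 and 85% at 0.95.

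**Continuous reading, margin 10 %EWL points.** n per arm = 2 × f × SD² / 10².

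| Assumed SD | n per arm | Total |
|---|---|---|
| 19 | 62 | 124 |
| 20 | 69 | 138 |
| 21 | 76 | 152 |

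So 138 needs an SD of about 20.

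**Intervals the sizing rule would call for.** These are descriptive, use available cases and take Table 2 at face value.

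- 12 months: A 63.7 ± 14.1 (n=67), B 59.6 ± 12.5 (n=69). Pooled SD 13.31, SE 2.283. A − B = 4.1, 90% CI 0.3 to 7.9.
- 24 months: A 62.8 ± 13.1 (n=65), B 61.6 ± 10.5 (n=66). Pooled SD 11.86, SE 2.073. A − B = 1.2, 90% CI -2.2 to 4.6.

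**Does the %EWL row fit the BMI row?** The documents do not define ideal weight, so reference BMIs of 20, 22 and 25 are assumed. From group means, %EWL ≈ 100 × (baseline BMI − follow-up BMI) / (baseline BMI − reference BMI).

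- Group A at 12 months: 43 − 24.2 = 18.8. Dividing by 23, 21 and 18 gives about 82, 90 and 104, against the printed 63.7.
- Group B at 12 months: 44 − 27.5 = 16.5. Dividing by 24, 22 and 19 gives about 69, 75 and 87, against the printed 59.6.
- B − A is then about -13 to -18, against the printed -4.1.
- A value of 63.7 in Group A would imply a reference BMI of 43 − 18.8/0.637 ≈ 13.5.

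This is a rough check: it uses group means, and baseline n is 75 against 67 and 69 at follow-up. It is enough to show that the two rows need reconciling before the %EWL row is relied on.

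**Separate item, which adds nothing to the weight of this one.** Table 2 prints P<0.05 for 12-month %EWL. Its own summaries give t = 4.1/2.283 = 1.80 on 134 df, two-sided p = 0.075 (Welch also 0.075). The most favourable rounding of the printed values gives 0.067. A difference of 1.978 × 2.283 = 4.5 would be needed. A rank test on the raw data could differ.

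**The case against.** **The two error rates can coexist.** A 90% two-sided interval for non-inferiority and a two-sided 5% difference test can stand in the same plan, and the sizing paragraph does state an interval rule. This stands. Sidedness alone is not the contradiction; the outcome type and the undeclared primary hypothesis are. The interval rule is nevertheless not carried into the analysis paragraph, and no interval is reported.

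**Nobody claims non-inferiority from p>0.05.** This also stands. The documents do not draw that conclusion, so the harm is potential.

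**Binary may simply be the wrong word.** An SD of 20 is a round number and a rate of 95.8% is not, which makes a mislabel plausible. It remains a conjecture, and SD 20 should not be written in unless the calculator record shows it.

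**The trial was underpowered.** A reader might infer this from the binary table. The documents do not support it: the rate is unknown, and under the continuous reading with SD 20 the stated power is reproduced (90.2% with 69 per arm).

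**Nothing is lost, because the observed limits clear -10.** A reader might infer this from the intervals above, in either direction of comparison. It requires -10 to mean %EWL points, which is nowhere stated, and it requires the %EWL row of Table 2 to be sound, which its own BMI row puts in doubt. At most it is conditional on reconciling Table 2.

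**The results already exist, so only reporting can change.** True, but reporting includes the primary conclusion.

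**Conclusion.** The contradiction holds as a matter of text. The stated 90% power and -10 rule belong to a binary outcome that the document neither defines nor analyses, while the declared primary outcome is continuous %EWL with no declared hypothesis, deciding time point or reference arm. The power cannot be verified for %EWL, and it is not shown to be inadequate. The figure of 138 fits only a rate of about 96% (or 4%) or an SD of about 20. This assumes a 10-point margin, equal arms and the normal-approximation formula. The point should be corrected before any primary conclusion is drawn, because the choice between hypotheses determines what the %EWL results can show.

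**What to change.** 1. State one primary hypothesis (non-inferiority or difference), one outcome scale, the deciding time point or points, and which group is the reference. Make the Background, section 2.2 and section 2.6 agree.
2. Recover from the calculator record the outcome type, the SD or rate, and the unit of -10. Then:
   - If the record shows continuous %EWL, replace the word binary. Report experimental minus reference with a two-sided 90% CI against -10 as the non-inferiority decision, and label any two-sided 5% difference test secondary.
   - If it shows a binary outcome, define the responder and apply -10 to the difference in responder rates. State in the Background and section 2.2 how that outcome relates to %EWL.
   - If there is no record, withdraw the 90% non-inferiority power for %EWL. Report the two-sided between-group difference with its CI under a named test.
3. Label as post hoc anything not documented before the data were seen.
4. Reconcile the %EWL and BMI rows of Table 2 before comparing any observed limit with -10.
5. As a separate item, recheck the 12-month P<0.05 under a named between-group test.

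The cost is a rewritten sizing paragraph, matching edits to the Background and section 2.2, one named test, the intervals for the deciding time points, and a check of Table 2 against the source data. The power claim may have to be withdrawn.

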	Group A (n=72)	Group B(n=73)	p>0.05	Group A(n=70)	Group B(n=71)	P<0.05	Group A(n=67)	Group B(n=69)	p	Group A(n=65)	Group B(n=66)	p>0.05
BMI	30.9 ± 5.32	34.7 ± 4.18	P<0.05	26.13 ± 7.32	31.06 ± 3.12	P<0.05	24.2 ± 3.4	27.5 ± 4.3	P<0.05	25.2 ± 4.4	26.2 ± 3.3	p>0.05
EBWL%	40.9 ± 8.1	31.60 ± 8.7	P<0.05	54.1 ± 11.3	48.20 ± 12.5	P<0.05	63.7 ± 14.1	59.6 ± 12.5	P<0.05	62.8 ± 13.1	61.6 ± 10.5	p>0.05

Results

Table 3 GERD Health-Related Quality-of-Life (GERD-HRQL) Score preoperative and postoperative scores

Patients	Preoperative 150/150		3 months follow-up 145/150		p >0.05	6 months follow-up 141/150		P <0.05	12 months follow-up 136/150		P <0.05	24 months follow-up 131/150		p >0.05
	Group A (n=75)	Group B (n=75)	Group A (n=72)	Group B (n=73)		Group A (n=70)	Group B (n=71)		Group A (n=67)	Group B (n=69)		Group A (n=65)	Group B (n=66)	
GERD HRQL Score<15			38(52.7%)	57(78%)	P <0.05	36(51.4%)	56(78.8%)	P <0.05	47(70.4%)	55(79.7%)	P <0.05	49(75.3%)	55(83.3%)	P <0.05
GERD HRQL Score >16<30	7(9.3%)	9(12%)	29(40%)	15(20.5%)	P <0.05	30(42.8%)	14(19.7%)	P <0.05	16(23.8%)	13(18.8%)	P >0.05	14(21.5%)	10(15.1%)	P >0.05
GERD HRQL Score >31	-	-	5(6.9%)	1(1.3%)	P <0.05	4(5.7%)	1(1.4%)	P <0.05	4(5.9%)	1(1.4%)	P <0.05	1(1.5%)	0	P <0.05
Significant Vomit	-	-	11(15,3%)	3(4.1%)	P <0.05	6(8.6%)	2(2.8%)	P <0.05	6(8.9%)	2(2.9%)	P <0.05	2(3.1%)	1(1.5%)	P <0.05
Intolerance to food	-	-	2(2.7%)	0	P <0.05	1(1.4%)	0	p >0.05	0	0	p >0.05	0	0	p >0.05

Table 4: Endoscopy Preoperative and at 1 and 2 years follow-up into two Groups

	Preoperative Patients 150		1 year follow-up Patients 108/150(72%)		2 years follow-up Patients 105/150(70%)	
	Group A 75	Group B 75	Group A 53	Group B 55	Group A 52	Group B 53
Esophagitis						
A	4(5.3%)	5(6.7%)	9(16.9%)	7(12.7%)	5(9.6%)	5(9.4%)
B	-	-	11(20.7%)	5(9%)	9(17.3%)	3(5.6%)
C	-	-	2(3.8%)	0	1(1.9%)	0
D	-	-				
Esophageal biopsy						
Metaplasia	-	-	0	0	0	0
Helicobacter Pylori	9(12%)	7(9.3%)				
Hiatal Hernia< 5 cm	1(1.3%)	2(2.7%)	-	-	-	-

Figure 1 Diagram of Patients eliability

Flow Diagram

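### The primary outcome (%EWL) has no formula, ideal weight or named between-group test; its printed 12- and 24-month values conflict with the printed BMI, and the 12-month P<0.05 is not reproduced

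*Combined protocol and SAP*

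**What the plan says.** Section 2.2 names the primary outcome: "Primary outcome was the evaluation of %EWL between 2 groups". The Background sets the time points at 1 and 2 years. Section 2.5 lists the recorded weight measures as "BMI (in kg/m²), %EWL and percentage total weight loss %TWL from baseline", with no formula, ideal weight or reference BMI. The Table 1 footnote only expands the abbreviation.

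Section 2.6 names two kinds of test: "Baseline comparisons were performed using chi-square tests and T-tests" and "Differences between preoperative and postoperative parameters were compared by Wilcoxon paired rank test". Neither is a between-group comparison at follow-up. The same section sets two-sided p<0.05 for all tests.

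Table 2 prints, Group A (2 cm) then Group B (6 cm):

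- %EWL, 12 months (n=67, 69): "63.7 ± 14.1 59.6 ± 12.5 P<0.05"
- BMI, 12 months: "24.2 ± 3.4 27.5 ± 4.3 P<0.05"
- %EWL, 24 months (n=65, 66): "62.8 ± 13.1 61.6 ± 10.5 p>0.05"
- BMI, 24 months: "25.2 ± 4.4 26.2 ± 3.3 p>0.05"

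Table 1 gives baseline BMI 43 ± 8 (range 40–57) in A and 44 ± 4 (40–55) in B, weight 124.5 and 125.3 kg, and height 150.1 ± 23 and 152.8 ± 33 (cm according to the pre-operative section).

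**The concern.** Height cancels within a patient, so once an ideal BMI is fixed, %EWL follows from baseline and visit BMI. The two rows of Table 2 should therefore agree for some sensible ideal BMI. They do not: a group whose mean BMI falls from 43 to 24.2 has lost nearly all, or more than all, of its excess under the usual references, yet 63.7% is printed. The printed 12-month P value also looks too small for its own means and SDs.

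At stake are the size of the primary effect at both time points and the claim of statistical significance at 12 months.

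**Working it through.** **1. The printed P values.** Two-sample t-test from the printed means, SDs and n. The choice of test is an assumption, since none is named.

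- %EWL, 12 months: pooled SD 13.31, SE = 13.31 × √(1/67 + 1/69) = 2.283, difference 63.7 − 59.6 = 4.1, t = 1.80 on 134 df, two-sided p = 0.075 (Welch 0.075), 95% CI −0.4 to 8.6. The most favourable rounding of the inputs gives p = 0.067. One-sided, p = 0.037. The printed P<0.05 is not reproduced two-sided.
- %EWL, 24 months: difference 1.2, 95% CI −2.9 to 5.3, p = 0.56. Agrees with its label.
- BMI, 12 months: difference −3.3, 95% CI −4.6 to −2.0, p ≈ 0.000002. Agrees.
- BMI, 24 months: difference −1.0, p = 0.14. Agrees.

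**2. %EWL implied by the BMI rows.** %EWL = 100 × (b − f)/(b − I), with b baseline BMI, f visit BMI and I ideal BMI (assumed, 18.5 to 25). Example, A at 12 months, I = 22: 100 × (43 − 24.2)/(43 − 22) = 89.5.

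| | I = 18.5 | I = 22 | I = 25 | Printed |
|---|---|---|---|---|
| A, 12 months | 76.7 | 89.5 | 104.4 | 63.7 |
| B, 12 months | 64.7 | 75.0 | 86.8 | 59.6 |
| A − B, 12 months | 12.0 | 14.5 | 17.6 | 4.1 |
| A, 24 months | 72.7 | 84.8 | 98.9 | 62.8 |
| B, 24 months | 69.8 | 80.9 | 93.7 | 61.6 |
| A − B, 24 months | 2.8 | 3.8 | 5.2 | 1.2 |

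Solving for the ideal BMI that fits, I = b − (b − f)/(%EWL/100): 12 months, A 43 − 18.8/0.637 = 13.5 and B 44 − 16.5/0.596 = 16.3; 24 months, A 14.7 and B 15.1. Over all four visits it runs from 11.8 to 17.2 and differs by arm and visit.

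**3. Can averaging, dropout or rounding explain it?** Write X = 1/(b − I). Mean %EWL = 100 × [1 − E{(f − I)X}], and E{(f − I)X} is at most (F − I)E(X) + SD(f)SD(X), where F is the mean visit BMI. Allow baseline ranges 39.5–57.5 (A) and 39.5–55.5 (B), baseline means ± 0.5, visit mean and SD + 0.05, and the worst possible dropout.

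Example, B at 12 months, I = 22:

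- Lowest completer mean: (75 × 43.5 − 6 × 55.5)/69 = 42.46.
- With all patients at the two range limits, a share (55.5 − 42.46)/16 = 0.815 sits at 39.5. So E(X) = 0.0521 and SD(X) = 0.0106.
- Bound: 100 × [1 − (5.55 × 0.0521 + 4.35 × 0.0106)] = 66.5, still above 59.6.

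Lowest attainable mean %EWL, 12 and 24 months:

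- I = 25: A 98.8, 91.1; B 77.9, 87.2.
- I = 22: A 84.4, 78.2; B 66.5, 74.2.
- I = 18.5: A 71.6, 66.4; B 56.9, 63.0.

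Every bound exceeds the printed value except B at 12 months with I = 18.5 (56.9 against 59.6).

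**4. Table 1 against itself.**

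- Mean weight over mean height squared: 124.5/1.501² = 55.3 (A) and 125.3/1.528² = 53.7 (B), against 43 and 44.
- Averaging does not explain this. Mean weight is at most mean BMI × E(h²) + SD(BMI) × SD(h²). With BMI rounding allowed and heights taken as roughly normal, that is 43.5 × 2.306 + 8.5 × 0.695 = 106.2 kg (A) and 44.5 × 2.444 + 4.5 × 1.020 = 113.3 kg (B).
- Group A's BMI SD: range 40–57 with mean 43 allows at most √[(57 − 43)(43 − 40) × 75/74] = 6.5. At the rounding limits, √(14 × 4 × 75/74) = 7.53, so the printed 8 is barely reachable.
- Total column: with equal arms, weight should be (124.5 + 125.3)/2 = 124.9 kg; 121.9 is printed, below both arms. BMI can be at most (43.5 + 44.5)/2 = 44.0; 44.23 is printed.

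**The case against.** Four points on the other side have weight.

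First, p = 0.075 rests on a test that the documents do not name. A rank test on patient data could give another value, and a one-sided test would give 0.037. The sample-size paragraph does speak of a one-sided interval, so a one-sided label is a possible source of the printed P, although it would breach the two-sided rule in 2.6. A reader might infer that the 12-month result is non-significant, or that the printed P is false. The documents support only that it is not reproduced and is unsettled.

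Second, a reader might take 12 to 18 points as the true 12-month difference. It is a ratio of means without an interval, and it rests on a baseline BMI row that is itself doubtful. Using the printed means, visit SDs and baseline ranges, opposite extreme pairing of baseline and visit BMI in the two arms moves it from 6.5 (72.9 − 66.4) to 19.1 (78.2 − 59.1) at ideal BMI 18.5, and from 8.3 to about 30 at 25. It is not a bound and not a rival estimate.

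Third, the height SDs of 23 and 33 cm are implausible for adults, so the weight–height check may show no more than a bad height row. That is possible, but it is still a data error, and the conflict between %EWL and BMI does not use height.

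Fourth, the weight and %TWL rows announced in Table 2's title are not visible in the extracted text. Their absence is not held against the plan, and they may help to settle which series is right.

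**Conclusion.** The point holds. The primary outcome is undefined, and its printed 12- and 24-month values cannot be reconciled with the printed BMI for an assumed ideal BMI of 22 to 25. At 18.5 only Group B at 12 months becomes reachable. Together with the inconsistencies in Table 1, this means that at least one of the height, weight, BMI and %EWL series is wrong. The documents do not show which, so it should not be read as proof that the %EWL row is the faulty one.

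Statistical significance is in doubt at 12 months only, and under an assumed two-sided t-test. At 24 months both rows are non-significant and match their labels, so there only the size is in question. The direction, A above B, is the same in both rows at both visits.

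The conclusion assumes one ideal BMI applied to all patients and the standard form of %EWL.

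**What to change.** 1. State in 2.5 the %EWL formula and ideal weight, and in 2.6 the between-group test and its sidedness, that actually produced the printed values.
2. Recompute BMI, %EWL and %TWL for each patient and visit from source height and weight. Check that the three agree, and correct Tables 1 and 2, including the Total column.
3. Re-run a named two-sided between-group comparison of %EWL at 12 and 24 months, reported with the difference and 95% CI. Correct the 12-month P if it is not below 0.05.
4. If the formula used cannot be recovered, adopt one named ideal weight (for example the weight at BMI 25), label the choice post hoc, and report %TWL beside it as a check that needs no ideal weight.
5. Base the primary conclusion only on the reconciled values.

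The cost is a source-data check and a re-analysis of data already collected, with no new measurements.
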